**Table 5. Data collection requirements for subject withdrawal**

Time of Early Withdrawal	Procedures Required
Prior to Device Activation	Complete appropriate visit eCRFs based on the visits completed (e.g. Baseline, Device Trial etc.) prior to discontinuation and the study exit eCRF.
After Device Activation and prior to the 12-Month/Final Visit	Complete all appropriate visit eCRFs based on visits completed prior to the discontinuation, the 12-Month/Final Visit eCRF (if subject is willing), and study exit eCRF.

## 9.20. Pregnancy

The safety of SCS has not been established for pregnant women, for an unborn fetus, or during childbirth. If a subject is able to become pregnant and is sexually active, documentation of medically acceptable birth control must be present in the medical records. In the event that a subject becomes pregnant during the study, it is not considered an AE; however, the study center must immediately inform Medtronic study personnel and perform the following activities:

- The investigator will instruct the subject to turn the stimulator “OFF” and to return to the site for a visit as soon as possible. The subject will be exited from the study.
- The study center must complete a Study Exit eCRF and final interrogation and upload reflecting therapy suspension.
- The Principal Investigator should notify the IRB per the study center’s specific requirements.

## 10. Risks and Benefits

### 10.1. Potential Risks

Spinal Cord Stimulation therapy is a reversible procedure (i.e., the system can be turned off or removed in most cases) with stimulation parameters that are adjustable to minimize or reverse complications and maximize therapeutic effects. The RestoreSensor SureScan MRI and Intelis AdaptiveStim Neurostimulation systems are commercially available for treatment of chronic intractable pain. The risks associated with the RestoreSensor SureScan MRI and Intelis AdaptiveStim Neurostimulation systems are included in commercial product information. Systems will only be used in geographies where they are commercially available. There are no expected new or increased risks associated with this clinical study.

There may be additional risks related to the use of Medtronic neurostimulation systems, other than the ones described below, that are not yet known.

### **10.1.1. Risks of Surgery**

Implanting a neurostimulation system has risks similar to spinal procedures, including spinal fluid leak (spinal fluid collection under the skin), headaches, swelling, bruising, bleeding, infection, or paralysis.

Subjects on anticoagulation therapy may be at higher risk for problems after surgery such as hematomas that could result in paralysis.

### **10.1.2. Spinal Cord Stimulation Risks**

The implantation of a spinal cord stimulation system involves risks that are similar to other spinal procedures. In addition to those normally associated with surgery, implantation or use of a neurostimulation system includes, but is not limited to, the following risks:

- Allergic or immune system response to the implanted materials
- Infection
- Lead or neurostimulator erosion through the skin or migration
- Leakage of cerebrospinal fluid
- Loss of pain relief may return patients to their underlying pain condition
- Persistent pain at the neurostimulator site
- Placement of the epidural lead is a surgical procedure that may expose patients to risks of epidural hemorrhage (bleeding), hematoma, or paralysis
- Radicular chest wall stimulation
- Seroma (fluid collection in pocket where stimulator is placed) or hematoma at the neurostimulator site
- Change in stimulation, possibly related to cellular changes around the electrode(s), shifts in electrode position, loose electrical connections, lead fractures, which has been described by some patients as uncomfortable stimulation (jolting or shocking sensation)
- Over time there could be changes in the level of symptom control. In most cases, the physician can correct these changes without surgery.
- Formation of excessive tissue around the lead in the epidural space can result in delayed spinal cord compression and paralysis, requiring surgical intervention. Time to onset can range from weeks to many years after implant.
- The safety of this therapy is unknown for pregnancy, unborn fetus, or delivery
- Stimulation-dependent gastrointestinal symptoms such as diarrhea, incontinence or constipation
- Stimulation-dependent bladder symptoms such as urinary retention, incontinence or frequency
- Unexpected changes in stimulation - Electromagnetic interference, changes in posture, and other activities can cause a perceived increase in stimulation

# Vectors Post Market Clinical Investigation Plan

[figure not shown]
#MDT17053

Version 4.0 08 May 2018

Page 49 of 80

[Redacted text block]

[Redacted text block]

**Low battery charge level** – Charge the neurostimulator when you see a **Low battery** screen displayed on the patient programmer or **recharger**. If the battery charge level is at 0, the device should be recharged to avoid therapy delivery falling to 0. For RestoreSensor SureScan MRI Neurostimulator if the battery remains in a discharged state, it continues to lose charge and it will become overdischarged. If the RestoreSensor SureScan MRI Neurostimulator battery is allowed to overdischarge, the recharger may not be able to recharge or communicate with the neurostimulator; however, your doctor may be able to restore the battery function. For RestoreSensor SureScan MRI Neurostimulator, follow the instructions in the model 37751 Recharger Charging System Manual to recharge the neurostimulator battery.

**Recharger use** – Check for skin irritation or redness near the neurostimulator during recharging. Do not sit or lie on the antenna or apply excessive pressure to the antenna. Take periodic breaks during prolonged recharging. Although no direct cause and effect has been established, some patients have reported heating sensation, discomfort, blistering not caused by heating, skin irritation, or redness near the implanted neurostimulator during or after recharging.

**Frequency of recharging**- per the patient programmer labeling subjects should check the battery level of their INS on a daily basis. Due to the higher pulse density of HD stimulation setting the recharging intervals may need to be more frequent. Daily activities may be disrupted based on the fact that subjects may need to recharge more frequently as a result of the programmed parameters used in this study. Subjects should pay particular attention to **Charging Efficiency** and **Battery Charge Level** indicators on the recharger.

- Check the neurostimulator battery charge level once a day or more frequently as needed.
- Keep the neurostimulator sufficiently charged to maintain therapy. It can be charged at any time; you do not need to wait for a low battery message.
- During neurostimulator recharging, monitor the Charging Efficiency row and adjust the antenna to obtain as many solid black boxes as possible. If only two boxes are filled in (6 or more boxes are empty) adjust the antenna to improve the signal strength between the neurostimulator and recharger.
- During recharging, ensure the neurostimulator Battery Charge Level is at least 25% before ending the charge session. However, a full battery charge is ideal.

### 10.1.5. Pregnancy Risks

Pregnant women are not able to take part in this study. Female subjects must agree to not become pregnant during the study by using a medically acceptable method of birth control. If a subject becomes pregnant during this study, there may be risks to the unborn child that are not yet known. The study doctor should be notified immediately if the patient thinks they are or have become pregnant. The stimulator will be turned "OFF" and the patient will be exited from the study.

### 10.1.6. Radiographic Imaging

As part of the study, subjects will be required to have fluoroscopic or X-ray images taken of their thoracic spine 1 time in addition to the imaging conducted to implant the leads. This may be beyond what is standard of care. The risk associated with these additional images has been considered and determined to be minimal since the total radiation dose will be approximately the same as one CT scan of the abdomen.

## 10.2. Study Risk Control Measures

The following will be done to mitigate risks associated with the implanted system:

- Investigators who are experienced with spinal cord stimulation implantation techniques will be utilized
- Instructions will be given to the study participants to ensure they can properly use the patient programmer and recharger system
- Subjects can turn off stimulation at any time during the study with the patient programmer or recharger
- Periodic monitoring of the study participants
- Labeling that contains precautions, warnings, and contraindications, as well as instructions on the use of the devices will be available and/or provided to the clinicians and subjects

## 10.3. Potential Benefits

Spinal cord stimulation may reduce low back or leg pain intensity, return the patient to a more fully functional status, and/or improve quality of life. Additionally, with stimulation delivered at comfort threshold amplitudes, subjects may avoid uncomfortable or even intolerable stimulation sensations, such as painful paresthesia. During the study subjects will have increased interaction with physicians or medical staff compared to routine clinical care, which may provide some indirect health benefits.

Data from this study may have the anticipated benefit of helping Medtronic with the understanding of SCS therapy and assisting with the design of future studies and product improvements. The information gathered from this study could also help clinicians optimize therapy for their patients.

## 10.4. Risk-Benefit Rationale

Neurostimulation therapies, such as SCS, are used as an aid in the management of chronic, intractable pain that cannot be effectively managed with medications and/or other conservative treatments alone. Patients considered for neurostimulation therapy have typically had pain of long duration and have failed multiple therapeutic paths. Findings from clinical studies documented in published literature suggest that T9/T10 has been a common location to target stimulation for chronic back and leg pain.

Medtronic has carefully designed and tested the RestoreSensor SureScan MRI and Intellis AdaptiveStim Neurostimulation Systems to ensure the safety and performance for the treatment of chronic, intractable pain. Medtronic has completed an extensive risk analysis to ensure the identification of potential hazards and subsequent mitigation of these hazards to eliminate them entirely or reduce them to an acceptable level.

The risks associated with the surgical implantation of the device, device use, and device failures are the same those observed for commercially available SCS devices. With an existing pre-market application approval for the commercially available RestoreSensor SureScan MRI and Intellis AdaptiveStim Neurostimulation Systems, an established safety profile of probable benefit outweighing risk already exists for SCS Therapy for chronic back and/or leg pain. In most cases implantation of SCS is a reversible procedure and the system can be turned off or removed. Moreover, stimulation parameters are adjustable to minimize or reverse complications and maximize therapeutic effects. System output and programming parameters used with the proposed HD stimulation parameters are within the range of the commercially available RestoreSensor SureScan MRI and Intellis AdaptiveStim Neurostimulation Systems. However, some subjects may not receive effective pain relief with the proposed HD stimulation parameters. HD stimulation non-responders will be managed in the same manner as commercial patients, and their devices may be programmed to any combination of parameters chosen by their physician. The anticipated benefits of the clinical outcomes of SCS therapy per the study design outweigh the overall risk.

## 11. Adverse Events and Device Deficiencies

### 11.1. Definitions/Classifications

Each adverse event is classified according to ISO 14155:2011 Where the definition indicates “device”, it refers to any device used in the study. See geography-specific addenda for applicable OUS information.

Term	Definition
------	------------

Adverse Event (AE): (ISO 14155:2011 3.2)
	
Any untoward medical occurrence, unintended disease or injury, or untoward clinical signs (including abnormal laboratory findings) in subjects, users or other persons, whether or not related to the investigational medical device.
 
NOTE 1: This definition includes events related to the investigational medical device or the comparator.
 
NOTE 2: This definition includes events related to the procedures involved.
 
NOTE 3: For users or other persons, this definition is restricted to events related to investigational medical devices.

Adverse Device Effect (ADE): (ISO 14155:2011 3.1)
	
Adverse event related to the use of an investigational medical device.
 
NOTE 1: This definition includes adverse events resulting from insufficient or inadequate instructions for use, deployment, implantation, installation, or operation, or any malfunction of the investigational medical device.
 
NOTE 2: This definition includes any event resulting from use error or from intentional misuse of the investigational medical device.

Device Deficiency (DD): (ISO 14155:2011 3.15)
	
Inadequacy of a medical device with respect to its identity, quality, durability, reliability, safety or performance.
 
NOTE: Device deficiencies include malfunctions, use errors, and inadequate labeling.

Malfunction: (ISO 14155:2011 3.27)
	
Failure of an investigational medical device to perform in accordance with its intended purpose when used in accordance with the instructions for use or (CIP).

Use Error: (ISO 14155:2011 3.43)
	
Act or omission of an act that results in a different medical device response than intended by the manufacturer or expected by the user.
 
NOTE 1: Use error includes slips, lapses, and mistakes.
 
NOTE 2: An unexpected physiological response of the subject does not in itself constitute a use error.

Term
	
Seriousness


Serious Adverse Event (SAE): (ISO 14155:2011 3.37)
	
Adverse event that
 
 
a) led to death,
 
b) led to serious deterioration in the health of the subject, that either resulted in             
 
1) a life-threatening illness or injury, or
 
2) a permanent impairment of a body structure or a body function, or
 
3) in-patient or prolonged hospitalization, or
 
4) medical or surgical intervention to prevent life-threatening illness or injury or permanent impairment to a body structure or a body function,
 
 
 
c) led to foetal distress, foetal death or a congenital abnormality or birth defect.
 

	NOTE: Planned hospitalization for a pre-existing condition, or a procedure required by the CIP, without serious deterioration in health, is not considered a serious adverse event.
Serious Adverse Device Effect (SADE):  (ISO 14155:2011 3.36)	Adverse device effect that has resulted in any of the consequences characteristic of a serious adverse event
Unanticipated Serious Adverse Device Effect (USADE):  (ISO 14155:2011 3.42)	Serious adverse device effect which by its nature, incidence, severity or outcome has not been identified in the current version of the risk analysis report.  NOTE: Anticipated serious adverse device effect (ASADE) is an effect which by its nature, incidence, severity or outcome has been identified in the risk analysis report.
Term	Relatedness
Device Related	An adverse event that results from the presence or performance (intended or otherwise) of the Neuromodulation System
Therapy Related	Event related to therapy delivery by device. Normally therapy-related events resolve when the device is turned off or reprogrammed. This category should not include events that resulted from a malfunction of the device (i.e. hardware-related events).
Procedure Related	An adverse event that occurs due to any procedure related to the implantation, surgical modification of the system or programming.

## 11.2. Foreseeable Adverse Events and Anticipated Adverse Device Effects

All anticipated adverse events and adverse device effects are the same as those foreseeable risks listed in Section 10.1.

## 11.3. Recording of Adverse Events

In this study, only device-, therapy- and procedure-related adverse events (AEs) and device deficiencies that occur from enrollment through subject discontinuation from the study will be collected. Adverse event and device deficiency information will be reported to Medtronic on an adverse event or device deficiency eCRF, one for each AE and/or device deficiency.

It is the responsibility of the investigator to identify the occurrence of device-, therapy- or procedure-related adverse events and device deficiencies and to ensure all required information is accurately recorded on the eCRF. Refer to the applicable eCRF for the information to be reported for each adverse event and device deficiency.

For adverse events that require immediate reporting, initial reporting to Medtronic may be done by phone, or e-mail, or on the eCRF by completing as much information as is available. The adverse event eCRF must be completed as soon as possible.

In case the investigator requires information from the sponsor in an emergency situation, the investigator can contact Medtronic using the contact details provided in the synopsis and Section 11.7.

The clinical course of each adverse event must be followed until the adverse event is resolved, the subject is in a stable condition, or until the subject discontinues from the study. "Ongoing" adverse events and device deficiencies must be assessed at each study visit. The adverse event eCRF should be updated when there is a change to the information provided on the form (e.g. change in intervention, outcome, relatedness, etc.).

At the last scheduled visit, the investigator will instruct the subject to provide an update on the status of any ongoing events and report any adverse event or issue with the device that they believe might be related to participation in the study.

## 11.4. Recording of Device Deficiencies

Device deficiency information will be collected throughout the study and reported to Medtronic on a device event eCRF, one for each device deficiency. The investigator must determine and document on the eCRF device deficiencies that did not lead to an adverse event but could have led to a serious adverse device effect:

- If either suitable action had not been taken
- If intervention had not been made, or
- If circumstances had been less fortunate

## 11.5. Adverse Event and Device Deficiency Reporting Requirements

only those Adverse Events (AEs) which are related to the following will be collected:

- The implanted SCS system, accessories and surgical procedures
- SCS therapy

In addition, all device deficiencies reported during the study will be collected.

It is the responsibility of the Investigator to adhere to the adverse event reporting requirements as stated within the protocol or in the applicable country-specific addenda and to their IRB/EC reporting requirements. Unanticipated Serious Adverse Device Effects (USADE) must be reported to Medtronic within 24 hours of learning of the effect, and to the IRB/EC as required. Medtronic is also responsible to report these events to participating investigators, IRBs/ECs, the FDA and or other regulatory agencies based on applicable local laws.

Upon receipt of notification of adverse events and device deficiencies at Medtronic, a Medtronic study team member will review for completeness and accuracy and when necessary, will request clarification and/or additional information from the investigator. If Medtronic disagrees with the Investigator’s assessment of the adverse event, Medtronic study personnel will document the disagreement and report or ensure reporting of both opinions to IRB/EC and regulatory agencies as required. Medtronic will utilize the Medical Dictionary for Regulatory Activities (MedDRA) to assign a MedDRA term for each adverse event and device deficiency based on the information provided by the investigator.

## 11.6. Non-Reportable Events

Events that are not reportable for this study are:

- Lack of pain relief
  - Pain symptoms will be collected as part of the efficacy measures
- Sensation of stimulation (paresthesia)
  - Sensation of stimulation (e.g. tingling, buzzing) will not be reported as this may occur as part of this therapy. **Exception: Sensation or stimulation events that are uncomfortable to the subject (e.g. shocking, jolting) will be reported.**
- Adverse events unrelated to
  - Implanted SCS system, accessories or surgical procedure
  - Spinal cord stimulation therapy

Table 6 provides a list of common expected surgical adverse events. An expected surgical event will not be considered reportable unless it worsens or is present outside the stated timeframe post-procedure.

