**Table 6: Expected Surgical Adverse Events and Durations**

Event description	Time frame after the surgical procedure
Anesthesia-related nausea/vomiting	24 hours
Mild to moderate pain at surgical site	7 days
Low-grade fever (<100°F or < 37.8°C)	48 hours
Mild to moderate bruising / ecchymosis	7 days
Pocket site / incisional pain	14 days
Seroma	72 hours
Sleep problems (insomnia)	72 hours

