7.10. Safety Evaluation

7.10.1. Adverse Events and Device Deficiencies

In this study, only device-, therapy- and procedure-related adverse events (AEs) and device deficiencies that occur from enrollment through subject discontinuation from the study will be collected. All AEs and device deficiencies will be summarized.

Adverse events and device deficiencies will be summarized by study phase (e.g., Pre-Trialing, Trialing, Implant), with the appropriate number of corresponding subjects as the denominator within each study phase as described below.

Adverse events and device deficiencies, referred to as “events” within this section, will be summarized separately. Events will be coded and summarized using the Medical Dictionary for Regulatory Affairs (MedDRA). Summaries will be presented as the number of events, the number of serious events (for adverse events only), the number of subjects who experienced the event, and the percent of subjects who experienced the event.

Each event summary will be presented in 2 ways (separate tables) using MedDRA’s coding system:

- (1) By MedDRA System Organ Class (SOC) and Preferred Term (PT), sorted first by the recommended SOC order, then in descending order within PT by percent of subjects, number of events, number of serious events (for adverse events), and then alphabetically by PT

- (2) By MedDRA PT, sorted in descending order by percent of subjects, number of events, number of serious events (for adverse events), and then alphabetically by PT.

Each adverse event is evaluated for whether it qualifies as an Unanticipated Serious Adverse Device Effect (USADE). All USADEs will also be summarized separately by study phase as described below. If no USADEs occur, a statement indicating that will be included.

In addition to the summaries above, device deficiencies may also be summarized by device type and PT. Detailed listings of all adverse events and device deficiencies will be included in the final study report.

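### The Table 6 exemption has no exception for serious events, so an expected surgical event that is serious from onset, does not worsen and resolves within its window is not reportable

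*Protocol*

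**What the plan says.** **The exemption.** Protocol 11.6 lists what sites do not report and ends with the expected surgical events of Table 6: "An expected surgical event will not be considered reportable unless it worsens or is present outside the stated timeframe post-procedure". Table 6 has seven rows, each with a time frame after the procedure. Some rows are limited by intensity, such as "Mild to moderate pain at surgical site". Others are not, such as "Anesthesia-related nausea/vomiting" (24 hours) and "Pocket site / incisional pain" (14 days).

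**An exception written elsewhere in 11.6.** Ordinary stimulation sensation is also exempt, but the protocol brings part of it back in bold: "Exception: Sensation or stimulation events that are uncomfortable to the subject (e.g. shocking, jolting) will be reported". Nothing comparable is written for a serious surgical event.

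**The SAE definition.** Protocol 11.1 defines an SAE by its outcome. One limb is a serious decline in the subject's health that results in, among other things, "in-patient or prolonged hospitalization". The accompanying note removes only planned admissions for an existing condition and procedures that the plan itself requires, and only where there is no such decline.

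**What is promised and counted.** Protocol 5.1.2 and 13.6 and SAP 4.2 undertake to characterize or summarize all events related to device, therapy or procedure, from enrollment to exit. SAP 7.10.1 includes in its summaries "the number of serious events (for adverse events only"), by study phase.

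**The concern.** Whether an event is serious depends on what it led to. Whether 11.6 makes it reportable depends on its trend and its duration. The two tests can disagree: an event may be serious on its first day, stay at that level and be over before its time frame ends. As written, 11.6 tells the site not to report it.

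The omission would happen at source. The SAP counts serious events among the adverse events collected, and it has no step for finding exempted ones. The study has no events committee or data monitoring committee, and under Protocol 12 the sponsor's medical advisor reviews reported events. A site that follows 11.6 has not deviated from the plan, so its silence would not ordinarily raise a query. The error has one direction: it can lower the reported serious-event rate and cannot raise it. It bears on the Trialing and Post-Implant safety tables, not on the primary or secondary objectives.

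**Working it through.** No stated sample size, power or alpha is at issue, so there is no figure of the plan's own to reproduce. The check is of the text, followed by a short illustration of scale.

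**1. Which rows lack a severity limit (Table 6)**

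| Row | Time frame | Intensity limit in the row |
|---|---|---|
| Anesthesia nausea/vomiting | 24 hours | none |
| Surgical-site pain | 7 days | mild to moderate |
| Fever | 48 hours | low-grade |
| Bruising | 7 days | mild to moderate |
| Pocket or incisional pain | 14 days | none |
| Seroma | 72 hours | none |
| Insomnia | 72 hours | none |

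Four of seven rows have no limit. In the other three the limit concerns intensity, which is not the same as seriousness but makes a serious case less likely.

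**2. Does another provision make a serious Table 6 event reportable?**

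- *11.3 and 11.5* call for procedure-related events to be collected. Neither says that it overrides 11.6.
- *11.5* sets a 24-hour duty for unanticipated serious adverse device effects (USADEs) only. Under 11.1 an event can be unanticipated by severity or outcome, so some Table 6 events might qualify. But a USADE must first be a device effect, and no rule says whether 11.5 or 11.6 prevails.
- *11.7* gives an emergency contact for serious device effects. It is not a reporting rule.
- *11.8* requires notice of every death.
- *13.6 and SAP 7.10.1 to 7.10.1.4* summarize what was collected and add no exception.

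What remains is a Table 6 event that is non-fatal, not clearly a USADE, serious from onset, not worsening, and over within its window. A possible case is vomiting after anesthesia that is severe at once, represents a serious decline in health, leads to an unplanned admission and settles within 24 hours.

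**3. How much of a safety phase one exemption can span**

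SAP 7.10.1.3 runs the Post-Implant phase from implant to just before activation. Protocol 9.5 schedules activation 9 to 16 days after implant. For activation on day d, the 14-day pocket or incisional pain row covers min(14, d)/d of that phase:

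- d = 9: 9/9 = 100%
- d = 14: 14/14 = 100%
- d = 16: 14/16 = 87.5%

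**4. What one omitted event would do (illustration; the documents give no rate)**

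Assume 100 subjects in the Implanted Analysis Set, which is the Post-Implant denominator; the plan aims for at least 100 through the 3-Month Visit. The Wilson 95% interval, which SAP 7.2 names for percentages of subjects, is

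[p + z²/2n ± z√(p(1−p)/n + z²/4n²)] / (1 + z²/n), with z = 1.96.

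- 0/100: upper limit z²/(n + z²) = 3.84/103.84 = 3.7%, so 0 to 3.7%
- 1/100: (0.0292 ± 0.0274)/1.0384, so 0.2% to 5.4%

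For the Trialing table the denominator is the Trialed Analysis Set. Its size is not stated, but by design it lies between 100 and the enrollment cap of 215. One omitted subject is then 1/215 = 0.5% to 1/100 = 1.0%.

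**The case against.** The strongest reply is that little is left once the safeguards are counted. An event that leads to a serious decline in health will usually have worsened, and 11.6 already makes worsening events reportable. Deaths are notified regardless. Table 6 is meant for minor, common events, and three of its rows are limited to mild-to-moderate or low-grade ones. The geography-specific addenda and the case report forms, which these documents do not include, may add reporting rules. All of this stands, and it makes the gap narrow. It does not close it: the plan does not define worsening, and on its ordinary meaning the word does not reach an event that is serious at the start.

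A reader might also infer more than the documents support:

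- *That any hospital stay makes a Table 6 event an SAE.* Protocol 11.1 requires a serious decline in health that results in the stay. An overnight admission alone is not enough, so the vomiting case above is a possible SAE, not a certain one.
- *That the exemption hides the serious surgical complications.* Spinal fluid leak, infection, epidural hemorrhage, hematoma and paralysis appear in 10.1.1 and 10.1.2 but not in Table 6. They stay reportable.
- *That an omitted event could never be recovered.* Monitors have access to source records under 15.1 and might see an admission. The fair statement is that nothing in the plan requires recovery.
- *That the exposure can be counted as three surgical procedures per implanted subject.* This treats removal of the trial leads as a surgical procedure, which the documents do not say. Exposure also differs by row: pocket pain concerns the permanent implant.
- *That one pooled serious-event rate per 100 implanted subjects is understated.* The SAP reports by phase, with a different denominator for each, and plans no such pooled rate.

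**Conclusion.** The point holds in a narrow form. Protocol 11.6 names two exceptions to the Table 6 exemption and seriousness is not one. No other provision in either document makes a Table 6 event reportable because it is serious. A non-fatal event that is serious from onset under 11.1, does not worsen and resolves within its window is therefore not reportable as written, chiefly in the four rows without a severity limit. It would be missing from the serious-event counts in SAP 7.10.1, contrary to the safety objective.

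The size is unknown and probably small. With an assumed denominator of 100, one omitted event would turn what should read 1% into 0% in the phase table concerned. That matters mainly because a statement of no serious events in a phase could be wrong. The conclusion assumes that sites apply 11.6 literally and that the unseen addenda and case report forms contain no overriding rule. It does not support a claim that serious surgical harm is broadly under-reported.

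**What to change.** In the last sentence of Protocol 11.6, add a third condition ahead of the existing two: that the event meets the definition of a serious adverse event in Section 11.1. An expected surgical event would then be reportable if it is serious, if it worsens, or if it outlasts its time frame. The Table 6 time limits stay as they are. The SAP needs no change, because its serious-event counts would then draw on complete reports.

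The cost is one clause in the next amendment, brief site retraining and a few more adverse event forms. The reported serious-event rate may come out slightly higher.
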